6.10 Contraceptive Requirements

Female of Childbearing Potential

A female is considered fertile following menarche and until becoming post-menopausal unless permanently sterile. Permanent sterilization methods include hysterectomy, bilateral salpingectomy, and bilateral oophorectomy.

Female in the following categories are not considered of child bearing potential:

1. Premenopausal female with 1 of the following:
 - a. Documented hysterectomy
 - b. Documented bilateral salpingectomy
 - c. Documented bilateral oophorectomy

Note: Site personnel documentation from the following sources is acceptable:

1) review of subject medical records, 2) subject medical examination, or 3) subject medical history interview.

2. Premenarchal female
3. Postmenopausal female
 - a. A postmenopausal state is defined as no menses for 12 months without an alternative medical cause. A high follicle stimulating hormone (FSH) level in the postmenopausal range may be used to confirm a postmenopausal state in women not using hormonal contraception or hormonal replacement therapy (HRT). However, in the absence of 12 months of amenorrhea, a single FSH measurement is insufficient.
 - b. Females on HRT and whose menopausal status is in doubt will be required to use 1 of the non-hormonal highly effective contraception methods if they wish to continue their HRT during the study. Otherwise, they must discontinue HRT to allow confirmation of postmenopausal status before study enrollment.

6.10.1 Female Subjects

Females of childbearing potential should be advised to avoid becoming pregnant while being treated with carfilzomib. Given that carfilzomib was clastogenic in the in vitro chromosomal aberration test in peripheral blood lymphocytes, as a precaution, FCBP and/or their male partners should use highly effective contraception methods or abstain from sexual activity during treatment and for 30 days after treatment with carfilzomib and for 3 months after cessation of daratumumab treatment.

Female subjects of childbearing potential must agree to use 1 highly effective method of contraception (as described in [Table 10](#)). It cannot be excluded that the efficacy of oral contraceptives may be reduced during carfilzomib treatment. In addition, due to an increased risk of venous thromboembolic events associated with carfilzomib, females should avoid the use of hormonal contraceptives that are associated with a risk of thrombosis during treatment with carfilzomib. Female subjects of childbearing potential

who are using oral contraceptives or a hormonal method of contraception that is associated with a risk of thrombosis should switch to an alternative non-hormonal method of highly effective contraception.

Table 10. Highly Effective Contraceptive Methods for Female Subjects

Failure rate of < 1% per year when used consistently and correctly

• Combined (estrogen and progestogen) hormonal contraception associated with inhibition of ovulation (oral, intravaginal [vaginal ring], or transdermal)• Progestogen-only hormonal contraception associated with inhibition of ovulation (oral, injectable, implantable)• Intrauterine device (IUD)• Intrauterine hormonal-releasing system (IUS)• Bilateral tubal ligation/occlusion• Vasectomized partner (provided that partner is the sole sexual partner of the female subject of childbearing potential and that the vasectomized partner has received medical assessment of the surgical success)• Sexual abstinence: Defined as refraining from heterosexual intercourse during the entire period of risk associated with the study treatments. The reliability of sexual abstinence must be evaluated in relation to the duration of the study and the preferred and usual lifestyle of the subject.

If a female subject is suspected of being pregnant, the protocol-required therapies must be stopped immediately and may not be resumed until absence of pregnancy has been medically confirmed.

Lactation

It is not known if carfilzomib is transferred into breast milk. If the subject is breastfeeding and wishes to be in this study, they will be required to discontinue nursing during study treatment and for an additional 30 days after stopping carfilzomib.

There is no information regarding the presence of daratumumab in human milk, the effects on the breastfed infant, or the effects on milk production. Human IgG is known to be present in human milk.

The developmental and health benefits of breast-feeding should be considered along with the mother's clinical need for daratumumab and any potential adverse effects on the breast-fed child from daratumumab or from the underlying maternal condition.

6.10.2 Male Subjects

If the male's sole sexual partner is of non-childbearing potential or has had a bilateral tubal ligation/occlusion, he is not required to use additional forms of contraception during the study. The definition of non-childbearing potential is provided above.

Male subjects with a partner of childbearing potential must agree to not father a child during treatment of carfilzomib and/or daratumumab and for an additional 90 days after the last dose of carfilzomib and/or daratumumab.

Contraceptive options for male subjects include:

- Sexual abstinence (defined as refraining from heterosexual intercourse during the entire period of risk associated with protocol-required therapies). The reliability of sexual abstinence must be evaluated in relation to the duration of the trial and the preferred and usual lifestyle of the subject, or
- Use of a condom during treatment of carfilzomib and/or daratumumab and for an additional 90 days after the last dose of carfilzomib and/or daratumumab.

The female partner is to use an acceptable method of effective contraception such as: hormonal, intrauterine device (IUD), intrauterine hormonal-releasing system (IUS), female barrier method (diaphragm, cervical cap, contraceptive sponge [a female condom is not an option because there is a risk of tearing when both partners use a condom]).

Male subjects must not donate sperm during treatment of carfilzomib and/or daratumumab and for an additional 90 days after the last dose of carfilzomib and/or daratumumab.

Male subjects with a pregnant partner must practice sexual abstinence or wear a condom to prevent exposure of the unborn child to carfilzomib through semen.

6.10.3 Unacceptable Methods of Birth Control for Male and Female Subjects

Birth control methods that are considered unacceptable in clinical trials include: periodic abstinence (calendar, symptothermal, post-ovulation methods), withdrawal (coitus interruptus), spermicides only, and lactational amenorrhea method.

Male and female subjects of childbearing potential must receive pregnancy prevention counseling and be advised of the risk to fetus if they become pregnant or father a child during treatment of carfilzomib and/or daratumumab and for 90 days after the last dose of carfilzomib and/or daratumumab.

Additional medications given during the study may alter the contraceptive requirements. These additional medications may require female subjects to use highly effective methods of contraception and for an increased length of time. In addition, male subjects may also be required alter the duration and/or methods of contraception. The investigator must discuss these topics with subjects.

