- 111 Absolute neutrophil count (ANC) $\geq 1 \times 10^9/L$ within 21 days prior to randomization. Screening ANC should be independent of granulocyte- and granulocyte macrophage-colony stimulating factor support for at least 1 week and of pegylated granulocyte stimulating factor for ≥ 2 weeks.
- 112 Hemoglobin ≥ 80 g/L within 21 days prior to randomization. Patients should not have received red blood cell (RBC) transfusions for at least 7 days prior to obtaining the screening hemoglobin.
- 113 Platelet count $\geq 75 \times 10^9/L$ ($\geq 50 \times 10^9/L$ if myeloma involvement in the bone marrow is $\geq 50\%$) within 21 days prior to randomization. Patients should not have received platelet transfusions for at least 7 days prior to obtaining the screening platelet count.
- 114 Calculated or measured creatinine clearance (CrCl) of ≥ 20 mL/min within 21 days prior to randomization based on standard formula such as the Cockcroft and Gault. (Subjects on dialysis are excluded)
- 115 Females of childbearing potential (FCBP) must have a negative serum pregnancy test within 15 days prior to first dose of study drug and a negative urine pregnancy test within the 24 hours prior to first dose
- 116 FCBP must agree to use highly effective method(s) of contraception, during the study and for 30 days following the last dose of carfilzomib administration or 3 months following the last dose of daratumumab administration, whichever is

later for subjects in the KdD arm; and 30 days following the last dose of carfilzomib administration for the Kd arm.

- 117 Male subjects who are sexually active with an FCBP must agree to use condoms (unless they have had a vasectomy with medical confirmation of surgical success) during carfilzomib and/or daratumumab treatment and for additional 90 days following the last carfilzomib and/or daratumumab administration.
- 118 Male subjects must agree to not donate sperm, during treatment and for an additional 90 days following the last carfilzomib and/or daratumumab administration
- 119 Subject has provided informed consent/assent prior to initiation of any study specific activities/procedures.

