- 229 Known human immunodeficiency virus (HIV) infection, hepatitis C infection (subjects with hepatitis C that achieve a sustained virologic response following antiviral therapy are allowed), or hepatitis B infection (subjects with HBsAg or core antibody that achieve sustained virologic response with antiviral therapy directed at hepatitis B are allowed)
- 230 Currently receiving treatment in another investigational device or drug study, or less than 28 days since ending treatment on another investigational device or drug study(ies). Other investigational procedures while participating in this study are excluded.
- 231 Pregnant or breastfeeding women, or women who are planning to become pregnant or breastfeed during treatment and for an additional 30 days after discontinuing treatment.
- 232 Ongoing graft-versus-host disease
- 233 Autologous stem cell transplant less than 90 days prior to randomization
- 234 Vaccination with live attenuated vaccines within 4 weeks prior to randomization
- 235 Subject likely to not be available to complete all protocol required study visits or procedures, and/or to comply with all required study procedures (eg, Clinical Outcome Assessment [COAs]) to the best of the subject and investigator's knowledge.
- 236 History or evidence of any other clinically significant disorder, condition or disease (with the exception of those outlined above) that, in the opinion of the investigator or Amgen physician, if consulted, would pose a risk to subject safety or interfere with the study evaluation, procedures or completion
- 237 Subjects with grade 3 or worse neuropathy within 14 days prior to randomization
- 238 Allogeneic stem cell transplant less than 100 days prior to randomization
- 239 Patients on any immunosuppressive therapy for graft versus host disease, even if it has resolved

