9.3 Pregnancy and Lactation Reporting

If a female subject becomes pregnant, or a male subject fathers a child, while the subject is taking carfilzomib report the pregnancy to Amgen Global Patient Safety as specified below.

In addition to reporting any pregnancies occurring during the study, investigators should report pregnancies that occur 30 days after the last dose of carfilzomib or 3 months after the cessation of daratumumab treatment. For male subjects, investigators should report pregnancies that occur during treatment and for an additional 90 days after the last dose of carfilzomib and/or daratumumab (whichever was given last).

The pregnancy should be reported to Amgen Global Patient Safety within 24 hours of the investigator's **awareness** of the event of a pregnancy. Report a pregnancy on the Pregnancy Notification **Form** ([Appendix C](#)). Amgen Global Patient Safety will follow-up with the investigator regarding additional information that may be requested.

If a female subject becomes pregnant during the study or within 30 days after the last dose of carfilzomib or within 3 months after the last dose of daratumumab, the investigator should attempt to obtain information regarding the birth outcome and health of the infant.

If the outcome of the pregnancy meets a criterion for immediate classification as a Serious Adverse Event (eg, female subject experiences a spontaneous abortion, stillbirth, or neonatal death or there is a fetal or neonatal congenital anomaly) the investigator will report the event as a Serious Adverse Event.

If a female breastfeeds while taking protocol-required therapies report the lactation case to Amgen as specified below. In addition to reporting a lactation case during the study, investigators should report lactation cases that occur 30 days after the last dose of carfilzomib or 3 months after the last dose of daratumumab.

Any lactation case should be reported to Amgen Global Patient Safety within 24 hours of the investigator's **awareness** of event. Report a lactation case on the Lactation Notification **Form** ([Appendix C](#)). Amgen Global Patient Safety will follow-up with the investigator regarding additional information that may be requested.

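### For women, the 90-day fetal-risk counselling window does not match the 30-day contraception window after carfilzomib, and Table 10 lists methods that the adjoining text restricts

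*Protocol*

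**What the plan says.** **Counselling.** Section 6.10.3 covers men and women together. They must "be advised of the risk to fetus if they become pregnant or father a child during treatment of carfilzomib and/or daratumumab and for 90 days", counted from the final dose of either drug.

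**Contraception.** Inclusion criterion 116 applies while the woman is in the study and then for a post-dose period. In the KdD arm that period is "30 days following the last dose of carfilzomib administration or 3 months following the last dose of daratumumab administration", whichever is later. In the other arm it is "30 days following the last dose of carfilzomib administration for the Kd arm". Section 6.10.1 uses the same two drug-specific periods, but counts them from treatment and does not mention the study period.

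**Pregnancy reporting.** Section 9.3 opens with pregnancies that arise while the subject takes carfilzomib; daratumumab is not named there. It then asks for any on-study pregnancy and adds that "investigators should report pregnancies that occur 30 days after the last dose of carfilzomib or 3 months after" daratumumab is stopped.

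**Choice of method.** Section 6.10.1 requires one highly effective method from Table 10. It also warns that oral contraceptives may work less well during carfilzomib and that "females should avoid the use of hormonal contraceptives that are associated with a risk of thrombosis" while on that drug. Women using oral or thrombosis-associated hormonal methods are told to change to a non-hormonal one. The first entry in Table 10 is "Combined (estrogen and progestogen) hormonal contraception associated with inhibition of ovulation", with oral, vaginal-ring and transdermal forms named. The second is progestogen-only contraception, oral form included. Neither entry carries a restriction.

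**Related text.** Exclusion 231 bars women "planning to become pregnant or breastfeed during treatment and for an additional 30 days after discontinuing treatment", with no distinction by arm or drug. The lactation paragraph of section 6.10.1 stops nursing during study treatment and for 30 days after carfilzomib, and gives no period after daratumumab. Section 9.3 asks for lactation cases up to 3 months after daratumumab.

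**The concern.** These passages instruct sites and subjects, and a site should be able to follow all of them at once. After the last dose the written windows are the main safeguard: section 7.3.16 and Table 11 place pregnancy tests at screening and on day 1 of each cycle, and the long-term follow-up contacts in section 7.2.5 are for survival and later therapy. If the period of stated risk is longer than the period of required contraception, a woman can comply fully and still conceive inside the stated risk period. If the required list of methods contains items that the neighbouring paragraph tells her to stop using, she can satisfy one instruction only by breaking the other. At stake are fetal exposure and complete pregnancy reporting. No efficacy estimate is involved.

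**Working it through.** The plan gives no calculated figure here to reproduce. The check sets the windows for women side by side (K = carfilzomib, D = daratumumab).

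| Purpose | Place | Kd arm | KdD arm |
|---|---|---|---|
| Counselling | 6.10.3 | 90 days after K | 90 days after K and/or D |
| Contraception | Criterion 116 | study, plus 30 days after K | study, plus the later of 30 days after K and 3 months after D |
| Contraception | 6.10.1 | treatment, plus 30 days after K | treatment, plus 30 days after K and 3 months after D |
| Pregnancy reporting | 9.3 | study, plus 30 days after K | study, plus 30 days after K or 3 months after D |
| Planned pregnancy or nursing | Exclusion 231 | 30 days after treatment | 30 days after treatment |
| Nursing | 6.10.1, lactation | treatment, plus 30 days after K | treatment, plus 30 days after K |
| Lactation reporting | 9.3 | study, plus 30 days after K | study, plus 30 days after K or 3 months after D |

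1. **Kd arm.** Counselling runs to day 90 and the post-dose contraception period to day 30: 90 − 30 = 60 days (days 31 to 90).

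2. **KdD arm, D stopped last.** Three calendar months are 89 to 92 days depending on the start date, so 3 months and 90 days differ by at most 2 days. There is no material conflict.

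3. **KdD arm, K stopped last.** Let the last D dose fall x days before the last K dose, and take 3 months as 90 days. Counted from the last K dose, required contraception ends on day max(30, 90 − x) and counselling on day 90. The difference is min(60, x) days: none when both stop together, 60 when D stopped 60 or more days earlier.

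4. **Does the study-period wording close the gap?** Criterion 116 and section 9.3 attach their windows to the study; section 6.10.1 attaches its window to treatment. The glossary ends an individual's study on the last day of protocol procedures, and follow-up contacts run every 12 weeks after treatment. On that broad reading, days 31 to 90 are covered for a woman still in follow-up, but the added 30 days then matter only if she leaves early. On the narrow reading, that the study means treatment, the 30 days is the real limit and the 60-day span is open. The text does not settle which is meant.

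5. **Table 10.** A woman who chooses an oral method meets the Table 10 requirement and at once falls under the instruction to change to a non-hormonal one. The same holds for any listed hormonal method that carries a thrombosis risk; the table does not say which ones do.

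6. **Exclusion 231 against criterion 116, KdD arm.** 89 − 30 = 59 to 92 − 30 = 62 days. Criterion 116 still binds a woman who passes 231.

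**The case against.** A reader might infer that the same women are given three conflicting windows: 30 days, 3 months and 90 days. The documents do not support that. The 30 days belongs to carfilzomib and the 3 months to daratumumab. Criterion 116 separates the arms and joins the two periods by taking the later, and 3 months is practically 90 days. The 90-day window for men is stated consistently.

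A reader might also infer a definite 60-day hole in pregnancy reporting for the Kd arm. That is too strong, because section 9.3 adds its post-dose windows to the reporting of any on-study pregnancy. A woman in survival follow-up may well be covered. What stands is that the coverage depends on an undefined phrase.

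On Table 10, the restriction sits just before the table and the two can be read together. Nor does the text bar every hormonal entry: injectable or implantable progestogen is affected only if it carries a thrombosis risk. The conflict is limited to oral products and thrombosis-associated methods, but for those it is direct.

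Exclusion 231 is a screening question about intentions, and any woman of childbearing potential who passes it must still meet 116, so the mismatch removes no protection. On nursing, the restriction already covers all study treatment, and a reporting window may properly be longer than a restriction. What remains is that no post-treatment nursing period is stated for daratumumab.

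Finally, section 6.10.3 is one pooled sentence whose 90 days matches the male window, and for Kd-arm women it errs toward caution. That may explain the mismatch, but a site still has two figures for one woman.

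**Conclusion.** Two conflicts hold on the text. First, women are counselled on fetal risk for 90 days after carfilzomib while the post-dose contraception period is 30 days. This leaves 60 days without a clear requirement in the Kd arm, and up to 60 days in the KdD arm when carfilzomib is the last drug stopped. Second, Table 10 offers, unmarked, oral and possibly other hormonal methods that the same section tells women to leave. Reporting over days 31 to 90 is ambiguous rather than absent, and the carfilzomib-only opening of section 9.3 adds to the doubt. The mismatches in exclusion 231 and in the nursing text are minor.

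The 60-day figure assumes that section 6.10.1, or the narrow reading of criterion 116, governs contraception. The number of women affected is not given. It is assumed to be small, because section 2.1 puts the median age at diagnosis of the disease at 70 years. PFS and the other efficacy analyses are unaffected. The documents do not show which window or list of methods is intended.

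**What to change.** The sponsor should reconcile inclusion criterion 116, exclusion 231, section 6.10.1 (including its lactation text and Table 10), section 6.10.3 and section 9.3. One table by drug, arm and sex, cited wherever the topic arises, should give a single window each for counselling, contraception, nursing and reporting. The text should define what the study period means in criterion 116 and section 9.3, and the opening sentence of section 9.3 should be aligned with the drug-specific windows that follow it. Table 10 should mark which entries fall under the restriction in section 6.10.1. The choice of windows and methods is for the sponsor's clinical and safety functions; none is proposed here.

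The cost is protocol wording, and consent wording where it repeats these windows. No new procedure or analysis change is needed.

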7. STUDY PROCEDURES

7.1 Schedule of Assessments

For Schedule of Assessments, please refer to [Table 11](#) and [Table 12](#). For the dosing schedule of investigational products and other protocol-required therapies in arm 1 and arm 2, please refer to [Table 13](#) and [Table 14](#), respectively.

Note that assessment cycles and dosing cycles both work to a 28-day cycle, but are independent ([Table 12](#)). [REDACTED], disease assessments should be obtained every 28 days from cycle 1 day 1, regardless of cycle duration including dose delays. [REDACTED]

[REDACTED].

Table 11. Schedule of Assessments

Assessment	Screening	Assessment Cycle Days							Follow-up ^a	LTFU	Notes
		1	2	8	9	15	16	22	Visit 1		
General Assessments											
Informed consent	X										
Demographics	X										
Medical/surgical history	X										Includes multiple myeloma history
Multiple myeloma frailty index	X										
Review of AEs/SAEs	Continually										Refer to Section 9.2.1.3 for AEs/SAEs that occur > 30 days after last dose of all study drug(s).
Concomitant medications	Continually										
Complete physical examination	X								X		
Physical measurements (weight, BSA)	X	X									BSA should be calculated per Mosteller formula and utilized to calculate required study drug doses. Weight can be measured again in case of substantial weight gain/loss.
Physical measurement (height)	X										
ECOG performance status	X								X		
12-lead ECG with QTc interval	X										And as clinically indicated.
ECG: cycle 1				X							
ECG: cycle 2		X									
Vital signs	X	X	X	X	X	X	X	(X)	X		Checked prior to administration of study drug(s) (K or D) in all cycles. Additional measurements described in Section 7.3.10. day 22 (arm 1 only): cycles 1 and 2 only.

(X) = Parentheses indicate that the particular test is situational at that time point, as specified in the respective notes. Footnotes defined on the last page of the table.

Table 11. Schedule of Assessments

Assessment	Screening	Assessment Cycle Days							Follow-up ^a	LTFU	Notes
		1	2	8	9	15	16	22	Visit 1		
General Assessments (continued)											
ECHO	X	(X)									Screening ECHO may be done within 30 days prior to randomization, if performed as a part of standard of care. Monitored every 6 months (\pm 2 weeks) from C1D1 (not to be assessed within 4 days of daratumumab infusion).
Pulmonary function tests (PFTs)	X	(X)									Screening PFT measurements may be done within 30 days prior to randomization, if performed as a part of standard of care. Monitored every 6 months (\pm 2 weeks) from C1D1 (not to be assessed within 4 days of daratumumab infusion).
Survival										X	Every 12 weeks (\pm 2 weeks) after last follow-up visit.
Subsequent Antimyeloma Therapies									X	X	Data on subsequent antimyeloma therapy will be collected regardless of whether the subject has progressed (see Section 7.3.14).
Laboratory Assessments											
Hematology: Screen/cycle 1	X	X		X		X		X			Screening: Subjects must fast for at least 9 hours. Lab results must be evaluated for potential dose modification assessment prior to dosing. Further details in Section 7.3.15.
Hematology: cycles 2+		X							X		
Chemistry: Screen/cycle 1	X	X		X		X		X			
Chemistry: cycles 2+		X							X		

(X) = Parentheses indicate that the particular test is situational at that time point, as specified in the respective notes. Footnotes defined on the last page of the table.

Table 11. Schedule of Assessments

Assessment	Screening	Assessment Cycle Days							Follow-up ^a	LTFU	Notes
		1	2	8	9	15	16	22	Visit 1		
Laboratory Assessments (continued)											
Coagulation tests	X										
Quantitative immunoglobulins	X										Repeated only in case of clinical need, such as recurrent infections.
Beta 2 microglobulin	X										
Pregnancy test (FCBP)	X	X									More frequent pregnancy tests may be conducted if required per local regulations.
Blood typing and IAT: arm 1 subjects only	X										A card with the results should be provided and subject should carry it throughout the treatment period and for at least 6 months after treatment ends
Anti-daratumumab antibodies: Cycles: 1, 7, 12		(X)									Arm 1 only. Scheduled samples are taken from PK sample.

(X) = Parentheses indicate that the particular test is situational at that time point, as specified in the respective notes.
 Footnotes defined on the last page of the table.

Table 11. Schedule of Assessments

Assessment	Screening	Assessment Cycle Days							Follow-up ^a	LTFU	Notes
		1	2	8	9	15	16	22	Visit 1		
Laboratory Assessments (continued)											
HBV testing		At the next scheduled site visit and every 12 weeks \pm 2 weeks or more frequently as clinically indicated through follow-up visit 1.							(X) Situational testing and monitoring will continue for subjects in arm 1 for a maximum of 6 months following the last dose of daratumumab.	Local hepatitis B testing (HBsAg, anti-HBs, and anti-HBc) will be performed at the next scheduled visit for all subjects that do not already have a known medical history of hepatitis B infection or who have not had testing conducted within the previous 12 weeks. See Sections 6.7.1 and 7.3.15 for additional information.	

Page 4 of 5

(X) = Parentheses indicate that the particular test is situational at that time point, as specified in the respective notes.
 Footnotes defined on the last page of the table.

Table 11. Schedule of Assessments

Assessment	Screening	Assessment Cycle Days							Follow-up ^a	LTFU	Notes
		1	2	8	9	15	16	22	Visit 1		
Optional Assessments (consent must be obtained)											
Pharmacogenetic analysis (saliva sample): cycle 1		X									Sample obtained prior to dosing on C1D1.
Pharmacogenetic analysis (bone marrow aspirate): cycle 1 and follow-up visit 1		X							(X)		One bone marrow aspirate sample (obtained prior to dosing on C1D1) can be used for FISH, MRD, and pharmacogenetic analyses. Follow-up sample collected only from subjects who achieve a CR or better while on study.
Biomarker assessment (plasma): Screen/cycle 1	X					(X)					Screening samples to be obtained prior to dosing on C1D1.
Biomarker assessment (plasma): cycles 3, 6, 13, and follow-up visit 1		(X)							X		Samples to be obtained on C1D15, C3D1, C6D1, C13D1, and follow-up. Also collected from consenting subjects who achieve a CR.
Biomarker assessment (serum): Screen/cycle 1	X					(X)					Screening samples to be obtained prior to dosing on C1D1.
Biomarker assessment (serum): cycles 3, 6, and follow-up visit 1		(X)							X		Samples to be obtained on C1D15, C3D1, C6D1, and follow-up.

(X) = Parentheses indicate that the particular test is situational at that time point, as specified in the respective notes.

AE = adverse event; ADA = anti-drug antibody; BSA = body surface area; CR = complete response; CxDx = cycle X day X; D = daratumumab;

ECG = electrocardiogram; ECHO = echocardiogram; ECOG = Eastern Cooperative Oncology Group; FCBP = female patients of childbearing potential;

FISH = fluorescence in-situ hybridization; HBV = hepatitis B virus; IAT = indirect antiglobulin test; K = carfilzomib; LTFU = long-term follow-up; LVEF = left ventricular

ejection fraction; MRD = minimal residual disease; PD = progressive disease; ██████████ PFT = pulmonary function test; PK = pharmacokinetics;

QTc = corrected QT (interval); SAE = serious adverse event.

^a Follow-up occurs: 30 days (+ 3) after the last administration of all study drug(s).

Table 12. Schedule of Disease Assessments

Assessment	Screening	Every 28 Calendar Days ^a (Starting From C1D1)	If Clinically Indicated	To Confirm PD	Notes
Disease Assessments					
Bone marrow sample for FISH and MRD[-]:	X	(X)			See Section 7.3.21.2 for additional timing details regarding FISH and MRD[-] assessments. Samples for MRD analysis are not required [REDACTED]
Bone lesion assessment	X		X	X	Within 30 days prior to randomization; will be repeated if worsening clinical symptoms suggest PD, or as clinically indicated.
Plasmacytoma evaluation	(X)	(X)	X	X	Will be done at screening only if clinically suspected. Screening evaluation may be done within 30 days prior to randomization, if performed as a part of standard of care. Assessment will be performed locally every 28 days (for physical exam) or every 12 weeks (for radiological exam).
SPEP/UPEP/immunofixation	X	X			Screening values may be used if within 14 days prior to C1D1. Post C1D1, UPEP and urine immunofixation will be measured every disease assessment.
SFLC	X	X			

(X) = Parentheses indicate that the particular test is situational at that time point, as specified in the respective notes.

CxDx = Cycle X day X; **DCO = data cutoff**; FISH = fluorescence in-situ hybridization; MRD = minimal residual disease; **OS = overall survival**; PD = progressive disease; PR = partial response; SFLC = serum free light chain; SPEP = serum protein electrophoresis; UPEP = urine protein electrophoresis.

^a [REDACTED], disease assessment should be performed every 28 ± 7 days until PD regardless of cycle duration including dose delays. Subjects who discontinue treatment prior to PD, but remain on study are required to complete the following assessments every 28 ± 7 days until PD. [REDACTED]

Table 13. Dosing Schedule - Arm 1 (KdD)

Investigational Products and Other Protocol-required Therapies	Dosing Cycle Day							Notes
	1	2	8	9	15	16	22	
IV predose and postdose hydration (for carfilzomib as needed)								
Cycle 1	X	X	X	X	X	X		Not required for days when daratumumab is administered
Dexamethasone IV or PO (40 mg/week)								
All cycles	20	20	20	20	20	20	40	Dexamethasone 40 mg will be taken weekly (20 mg each day when taken on successive days). Cycle 1: All subjects, regardless of age, will receive 20 mg C1D1 and C1D2, followed by 20 mg methylprednisolone on C1D3.
Dexamethasone IV or PO (20 mg/week) – for subjects > 75 years of age								
Cycle 1	20	20	20	8	20	8	20	Cycle 1: All subjects will receive 20 mg C1D1 and C1D2, followed by 20 mg methylprednisolone on C1D3. 20 mg will be given as a preinfusion medication for daratumumab infusion, followed by 8 mg of dexamethasone prior to carfilzomib infusion on C1D9 and C1D16. Cycle 2+: 20 mg must be given as a preinfusion medication for daratumumab infusion (without 8 mg dose on subsequent carfilzomib dosing day), otherwise the 20 mg dose can be split across carfilzomib dosing days (eg, 12/8, 10/10, etc).
Cycle 2	20	-	20	-	20	-	20	
Cycles 3 to 6	20	-	12	8	20	-	20	
Cycles 7+	20	-	12	8	12	8	20	
Carfilzomib IV								
Cycle 1	20	20	56	56	56	56		The dose ^a will be 20 mg/m ² on C1D1 and C1D2 and 56 mg/m ² beginning on C1D8 and thereafter.
Cycle 2+	56	56	56	56	56	56		
Daratumumab IV								
Cycle 1	8	8	16		16		16	For pre/post-infusion medication guidance, see Sections 6.2.2.1.1 and 6.2.2.1.2. C1D1 and C1D2: 8 mg/kg in 500 mL NS will be administered each day. Thereafter, daratumumab will be given 16 mg/kg per dose diluted in 500 mL NS. Daratumumab infusions begin after carfilzomib infusions are completed.
Cycle 2	16		16		16		16	
Cycles 3 to 6	16				16			
Cycles 7+	16							

CxDx = cycle X day X; IV = intravenous; KdD = carfilzomib, dexamethasone, and daratumumab; NS = normal saline; PO = by mouth.

^a For patients with baseline chronic hepatic impairment (mild, moderate), reduce the starting and subsequent doses of carfilzomib by 25% (ie, 15 mg/m² day 1 and 2 of cycle 1 and 42 mg/m² day 8 cycle 1 and thereafter).

Table 14. Dosing Schedule - Arm 2 (Kd)

Investigational Products and Other Protocol-required Therapies	Dosing Cycle Day							Notes
	1	2	8	9	15	16	22	
IV predose and postdose hydration (for carfilzomib as needed)								
Cycle 1	X	X	X	X	X	X		See Section 6.2.1.1.1 for details.
Dexamethasone IV or PO								
All cycles	20	20	20	20	20	20	40	When multiple doses are required within the same week, split the dose amongst the days for a total of 40 mg/weekly. The dexamethasone dose must be given as IV on C1D1 and C1D2.
Dexamethasone IV or PO – for subjects > 75 years of age								
All cycles	12	8	12	8	12	8	20	When multiple doses are required within the same week, split the dose amongst the days for a total of 20 mg/week (eg, 12/8, 10/10, etc). The dexamethasone dose must be given as IV on C1D1 and C1D2.
Carfilzomib IV								
Cycle 1	20	20	56	56	56	56		The dose ^a will be 20 mg/m ² on C1D1 and C1D2 and 56 mg/m ² beginning on C1D8 and thereafter.
Cycle 2+	56	56	56	56	56	56		

CxDx = cycle X day X; IV = intravenous; Kd = carfilzomib and dexamethasone; PO = by mouth.

^a For patients with baseline chronic hepatic impairment (mild, moderate), reduce the starting and subsequent doses of carfilzomib by 25% (ie, 15 mg/m² day 1 and 2 of cycle 1 and 42 mg/m² day 8 cycle 1 and thereafter).

